6.7 BASELINE, TIME WINDOWS AND CALCULATED VISITS

Baseline is defined as the last observation at, or prior to Visit 2. Hence, if a subject is randomized at Visit 2, but does not start trial medication until a future visit (e.g., Visit 4), then his/her baseline is the latest assessment performed at Visit 2. However, for laboratory safety measurements, the last value prior to the first drug administration will be considered as the baseline value.

Planned and actual test days are included in the analysis data sets and are calculated relative to the beginning of treatment as indicated in Table 6.7: 1 below.

For efficacy measurements, only one observation per time window will be selected for statistical analysis –the first one in the corresponding time window. If there are two observations which have the same difference in days to the planned day, or if there are two observations on the same day, the first value will be selected. If an observation is available on the last day of treatment, this observation will be preferably selected over any later observation that is still within the time window. Assignment of efficacy observations to visits based on time windows will be based on the non-imputed (observed) data. Repeated and unscheduled efficacy measurements will be assigned to the nominal visits according to the time windows described in Table 6.7: 1.

For safety measurements, data collected at all visits will be used. For repeated and unscheduled safety measurements for the same visit on treatment, the worst of these will be selected for analysis. In the case for which there is no standard reference direction for the safety parameter, the average of all values for the same visit will be used for analysis.

Visit	Relative to treatment start	
	Planned test day	Actual test day
2	1	Day 1 – Day 2

Table 6.7: 1Planned and actual study days

c42059532-01

Proprietary confidential information © 2023 Boehringer Ingelheim International GmbH or one or more of its affiliated companies.

3	8	Day 3 – Day 12
4	15	Day 13 – Day 19
5	22	Day 20 – Day 26
6	29	Day 27 – Day 33
7	36	Day 34 – Day 40
8	43	Day 41 – Day 47
9	50	Day 48 – Day 52
10/EOT	57 for completed subjects	Day 53 – treatment stop date (stopdt) + 7 days
eEOT	N/A (for early discontinued subjects)	Date of the last administration of trial medication + 7 days (for early discontinued subjects).
		The number of days will be assigned to the visit. Thus, if days to eEOT is 31, it will be mapped to Visit 6. For those that early discontinue treatment but continue with the collection of efficacy data, those data points will be mapped to the later Visits as per the above Visit window. Hence, if this same subject collects CAPS-5 at Day 46, it will be mapped to Visit 8.
End of Trial	EOT + 28 days	[stopdt + 8 days] to [stopdt + 30 days]

- Days are counted relative to the day of randomization, which is defined as Day 1.

- stopdt stands for treatment stop date.

There's no visit window mapping for C-SSRS given that it is collected every week throughout the study.

Proprietary confidential information © 2023 Boehringer Ingelheim International GmbH or one or more of its affiliated companies.

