Day	-28 c V anytir to 8 befor	l A ne up days	13	8±2	15±2	22±2	29±2	36±2	43±2	50±2	57+2		EOT / (Early drug discon- tinuation date) plus 28+2 days	
Additional Patient Asses	sments/P	rocedur	es											
Patient informational video placebo response mitigation ⁷		х												5 min
Patient training video speech recording ⁷		х												5 min
Training on Smartphone App ⁸		х												10-15 min
Drug intake adherence monitoring ⁹					← all IN	MP intake	at clinica	al site and	at home)				5 min
EcMA assessments ¹⁰				← perf		-	weekly fo				5-10 min			

Boehringer Ingelheim BI Trial No.: 1402-0030 c34993667-05 Clinical Trial Protocol

09 Jun 2023

Page 16 of 148

Proprietary confidential information © 2023 Boehringer Ingelheim International GmbH or one or more of its affiliated companies

At the screening visit, all clinical examinations and procedures as per Flow Chart 1 should be performed first, followed by PCL-5 (version comprising LEC, Extended Criterion A and PCL5),CAPS-5 and MINI, followed by the other clinical outcome assessments, listed in Flow Chart 2. Blood draws are preferably done after clinical outcome assessments and procedures is described in detail in section 6.2.

For all further clinical visits, please refer to section 6.2.2 for details on order of assessments and procedures.

- 1 Eligibility of patients is to be confirmed before Visit 1A is scheduled. Visit 1A must be scheduled at minimum 8 days prior to V2 to allow for 7 days of EcMA assessments before randomization. The randomization visit V2 should be planned shortly (preferably within the same week) after completion of the 7 day EcMA baseline assessment period.
- 2 Visits 3, 5, 7 and 9 will be conducted via telephone or by video call, if in line with local regulation.
- 3 Day of Randomisation / Day of first intake of randomized medication all activities, except postdose PK sampling, should be done before drug administration. For exceptions please refer to section 6.2.2.
- 4 The CAPS-5 past month version will be used at the screening visit for PTSD diagnosis and eligibility assessment. At the randomization visit V2 and at all subsequent study visits, the CAPS-5 past week version will be used.
- 5 C-SSRS: Columbia Suicide Severity Rating Scale baseline/screening version used at Screening, Columbia Suicide Severity Rating Scale since-last-visit version used for all subsequent study visits

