5.4.5 Other safety parameters

5.4.5.1 Assessment of Suicidality

C-SSRS - Columbia-Suicide Severity Rating Scale

Suicidal risk assessed by the C-SSRS. The C-SSRS is a semi-structured, investigator-rated interview, developed by clinical experts in cooperation with the FDA, assessing both suicidal behavior and suicidal ideation. It does not give a global score, but provides some categorical and some severity information specifically for behavior and ideation.

Page 75 of 148

Proprietary confidential information © 2023 Boehringer Ingelheim International GmbH or one or more of its affiliated companies

The C-SSRS is completed by the interviewer and is captured using the rater station/tablet provided by the vendor.

The C-SSRS has been widely used in large multinational clinical trials. The C-SSRS will be administered first at screening (Visit 1) (using the 'Baseline / Screening' version) with the aim to exclude patients with active moderate or severe symptomatology within a specified time prior to screening (i.e. 3 months for suicidal ideation and 1 year for suicidal behavior). The lifetime history of suicidal ideation and behavior will also be recorded.

After screening (Visit 1) the assessment 'since last visit' will be performed at each trial visit i.e. clinic and phone visits as per Flow Chart 2 ('Since Last Visit version'). The investigator is to review/consider the C-SSRS results for plausibility and clinical relevance. If the positive report is confirmed, appropriate actions for the patient's safety have to be initiated.

An experienced clinician can use the C-SSRS after a short training session. It takes approximately 5 minutes to administer and rate the C-SSRS. At a minimum, the interview consists of 2 screening questions related to suicidal ideation and 4 related to suicidal behavior, and may be expanded to up to 17 items in case of positive responses. Freetext entries are allowed; the investigator has to directly evaluate the scale and write a report.

All C-SSRS reports of suicidal ideation type 4 or 5 and all reports of suicidal behavior during the course of trial participation must be reported as separate SAEs by the investigator.

For 'Self-injurious behavior, no suicidal intent' standard AE/SAE reporting rules are to be applied.

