7.2 PLANNED ANALYSES

7.2.1 General considerations

The following patient analysis sets are defined for this trial:

- Full Analysis Set (FAS): includes all randomized patients who received at least one
 dose of trial medication during the trial and had a baseline and at least one postbaseline observation for the primary or secondary endpoints. The FAS is used for
 efficacy analyses and patients in FAS are analysed under the randomized trial
 medication.
- Treated Set (TS): includes all patients who signed informed consent and were treated with at least one dose of the trial medication. Patients in TS are analyzed under the actual trial medication received at randomization. The TS is used for safety analyses as well as demographics and baseline characteristics.

Data from patients who were screened but not randomized will be listed but not included in any summary or inferential statistics.

In general, baseline values are the last measurements taken prior to the first administration of trial medication at randomization (Visit 2), (see Flow Chart 1). Further details (e.g., the handling of randomized patients that receive the wrong treatment) will be provided in the TSAP.

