Vital signs, physical examinations, or other safety-relevant data observed at screening, baseline, during the trial and at the end-of-trial evaluation will be assessed with regard to possible changes compared to findings before start of treatment.

For more details, please refer to the TSAP.

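### The SAP's baseline rule gives the C-SSRS a look-back of one to four weeks, so ideation known from screening can read as absent at baseline and any comparison with that baseline can show it as new

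*SAP*

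**What the plan says.** SAP 6.7 sets the general rule: "Baseline is defined as the last observation at, or prior to Visit 2". It then makes one exception: "However, for laboratory safety measurements, the last value prior to the first drug administration will be considered as the baseline value". Its only other remark on the C-SSRS is that no visit windows apply to it. The general rule in protocol 7.2.1, the last measurement before first dose, leads to the same visit, so the two documents do not disagree here.

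Protocol Flow Chart 2 schedules the C-SSRS at Visits 1, 1A and 2 and at every later visit. Protocol 5.4.5.1 uses the Baseline/Screening version at Visit 1, to screen on 3 months of ideation and 1 year of behaviour, and adds: "The lifetime history of suicidal ideation and behavior will also be recorded". From then on the form changes: "After screening (Visit 1) the assessment 'since last visit' will be performed at each trial visit". Flow Chart 2, footnote 5, agrees: "Columbia Suicide Severity Rating Scale since-last-visit version used for all subsequent study visits".

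For the analysis, protocol 7.2.6 plans descriptive summaries of the C-SSRS. It also says that safety-relevant data, including data from screening and baseline, "will be assessed with regard to possible changes compared to findings before start of treatment". SAP 7.8 adopts protocol 7.2.6. SAP Table 7.9.3:1 lists C-SSRS suicidality in the interim package. SAP 7.2 takes pre-study suicidal ideation and behaviour out of the concomitant diseases and puts them in stand-alone tables.

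**The concern.** A last-value rule suits a measurement of current state. It does not suit a scale whose look-back changes from one visit to the next. On the C-SSRS, the last pre-dose form carries the shortest history and the first carries the longest. The rule therefore keeps a report covering one to four weeks and sets aside the screening report covering 3 months.

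The affected patients are admitted by design. Exclusion criterion 11 removes type 4 or 5 ideation in the 3 months before screening, at screening or at baseline, while recent type 1 to 3 ideation is allowed. Such a patient may report ideation at Visit 1, none between Visit 1A and Visit 2, and the same ideation again at Week 3. Set against the SAP baseline, the Week 3 report looks new.

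Suicidality by C-SSRS is a named safety assessment in protocol 2.2.3, and the safety profile feeds the sponsor's decision to stop or continue at the interim. The on-treatment side is asked every week for 8 weeks, so a short baseline makes recurrence look like onset.

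**Working it through.** The plan gives no figure to reproduce. The check has two steps.

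**1. Which form is the baseline, and what does it cover?**

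| Visit | C-SSRS form | Period covered |
|---|---|---|
| 1 | Baseline/Screening | 3 months for ideation, 1 year for behaviour, plus lifetime |
| 1A | Since last visit | Visit 1 to Visit 1A |
| 2 | Since last visit | Visit 1A to Visit 2 |

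The last observation at or before Visit 2 is the Visit 2 form. Flow Chart 2, footnote 1, puts Visit 1A at least 8 days before Visit 2. Protocol 6.2.1 limits screening to 28 days from Visit 1, and Visit 1A follows Visit 1, so the gap is under 28 days. Taking 3 months as 91 days, the Visit 2 form covers 8/91 = 9% to 27/91 = 30% of the ideation look-back at Visit 1. Footnote 1 also asks for Visit 2 soon after the 7-day app assessment, so gaps near the lower end are the more likely.

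**2. How often could earlier ideation then appear as new?** The documents give no rates, so this is an illustration. Assume an ideation-prone patient with a constant, independent weekly probability p of type 1 to 3 ideation and no drug effect. Let w be the Visit 1A to Visit 2 gap in weeks. Treatment lasts 8 weeks and the Visit 1 look-back is 13 weeks.

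- Appears new under SAP 6.7: A = (1−p)^w × [1−(1−p)^8]
- Appears new with the look-back included: B = (1−p)^(13+w) × [1−(1−p)^8]
- Excess due to the rule: A − B = (1−p)^w × [1−(1−p)^13] × [1−(1−p)^8]

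For p = 0.10 and w = 8/7: A = 0.887 × 0.570 = 0.505; B = 0.505 × 0.254 = 0.128; excess = 0.377.

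| p per week | Gap | A | B | Excess (points) |
|---|---|---|---|---|
| 5% | 8 days | 0.317 | 0.163 | 15 |
| 10% | 8 days | 0.505 | 0.128 | 38 |
| 20% | 8 days | 0.645 | 0.035 | 61 |
| 5% | 27 days | 0.276 | 0.142 | 13 |
| 10% | 27 days | 0.379 | 0.096 | 28 |
| 20% | 27 days | 0.352 | 0.019 | 33 |

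B leaves out any interval between Visit 1 and Visit 1A. Including it would lower B and slightly raise the excess.

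**The case against.** The strongest reply is that no visible analysis uses this baseline to count anything. Protocol 7.2.6 plans descriptive C-SSRS summaries, SAP 7.9.3 only names the output, and neither defines a new-onset, emergent or shift category. Sections of the SAP are also not visible, including appendices it cites, so a C-SSRS derivation may exist there. This stands. A reader might infer that the plan will count recurrent ideation as new; the visible text shows only that it could. It does not remove the point. Protocol 7.2.6 puts a comparison with pre-treatment findings in scope if its reference to other safety-relevant data covers the C-SSRS. That is the natural reading, since protocol 5.4.5 places the scale under other safety parameters. The only visible baseline for that comparison is the one in SAP 6.7.

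Several narrower replies also stand:

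- Screening history is not lost. Protocol 5.4.5.1 treats it as a baseline condition, SAP 7.2 tabulates it and SAP 7 lists individual values. However, nothing visible links those tables to the on-treatment summary.
- Adverse-event tables do not use this baseline. Type 4 or 5 ideation and suicidal behaviour on treatment are reported as SAEs regardless.
- Exclusion criterion 10 removes suicidal behaviour in the year before screening and during screening, so the 1-year behaviour look-back changes little in correctly enrolled patients.
- Ideation that persists between Visit 1A and Visit 2 is captured at Visit 2.

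A reader might also infer that the rule biases the drug comparison or hides a drug signal. The documents do not support that. The rule acts alike on both randomised arms and the safety analyses are descriptive. Added background can blur a contrast, but by how much is unknown.

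**Conclusion.** The point holds as a poor baseline choice for one scale. As written, SAP 6.7 makes the Visit 2 since-last-visit form the C-SSRS baseline. Permitted type 1 to 3 ideation from Visit 1 or Visit 1A that does not recur before Visit 2 then reads as absent, and a comparison with that baseline can present its return as new.

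No trial-level rate can be given, because the documents state neither how many patients are prone to ideation nor how often it recurs. The excess of 13 to 61 points applies to one ideation-prone patient under assumed weekly probabilities of 5% to 20%, independence between weeks and gaps of 8 to 27 days. Column A, for example 32%, 50% and 65% at 8 days, should not be read as the misclassification rate: it includes patients with no ideation in the look-back, who would count as new under the better baseline too. The change is worth making before unblinding because suicidality is a named safety assessment and enters the interim review.

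**What to change.** Add a C-SSRS exception to SAP 6.7, beside the laboratory one. Baseline is the worst category over all pre-dose assessments: the recent look-back at Visit 1 (3 months for ideation, 1 year for behaviour), Visit 1A and Visit 2. Show lifetime history separately. In SAP 7.8, state that on-treatment ideation or behaviour will be summarised as new or worsened against that baseline, and apply the same definition in the interim package. Keep a by-visit summary so that the state immediately before dosing stays visible. If a section not shown here already holds such a rule, a cross-reference from SAP 6.7 is enough.

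The cost is a few sentences and minor programming. All the data are already collected, and no visit or assessment changes.

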6. GENERAL ANALYSIS DEFINITIONS

6.1 **TREATMENT(S)**

For details on the treatment regimen, assignment of treatment groups, and the selection of doses, refer to Section 4 of the CTP. Below in Table 6.1:1 are the descriptions of the short and long names of the treatments. Next, are the definitions of the study phases for the analysis periods (Table 6.1:2).

Table 6.1: 1 Treatment descriptions

Long Name	Short Name	
Placebo	Placebo	
BI 1358894 125 mg qd	BI 125 mg	

Table 6.1: 2 Study analysis phases*

Study analysis phase	Description	Start Date (included)	End Date (included)
Screening phase	Screening (prior to treatment)	Date of informed consent	Date of first treatment administration minus 1 day
Treatment phase and residual effects period	On-treatment period	Date of first treatment administration	Date of last treatment administration + REP
Follow-up phase	Off-treatment period	Date of last treatment administration + REP +1 day	Date of last CTP visit

* The defined treatment periods are the same for all treatment groups.

REP is the residual effect period which is defined as 28 days after the last dose of trial treatment for safety, and 7 days after last dose for efficacy

Dates are defined individually per patient. If more than one date is associated with a specific visit, measurements associated with a specific date are assigned to a study analysis phase according to the rules specified in the table. An analysis phase will not extend beyond the start date of the following phase.

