6.3 INTERCURRENT EVENTS

The following intercurrent events (ICEs) are of interest:

- 1. Change in background CNS active medication (e.g., non-SSRI antidepressant, anxiolytics)
- 2. Change in pharmacological therapy (SSRI)
- 3. Change in drug test result from negative to positive (Benzodiazepine, Barbiturates, Opiates, Cocaine, Amphetamines, Methadone, PCP)
- 4. Change in non-pharmacological therapy trauma-focused psychotherapy
- 5. Change in non-pharmacological therapy all other cognitive/behavioral therapy (CBT) (e.g., any other kind of psychotherapy, nicotine withdrawal therapy, diet, etc.)
- 6. Withdrawal of study medication due to investigator assessed drug-related adverse events (e.g., headache)
- 7. Withdrawal of study medication due to perceived lack of efficacy or disease worsening
- 8. Withdrawal of study medication due to other adverse events
- 9. Withdrawal of study medication due to any other reasons.

Table 6.3:1 lists the handling of the ICEs for the primary estimand and supplementary estimand.

Proprietary confidential information © 2023 Boehringer Ingelheim International GmbH or one or more of its affiliated companies.

	ICE	Primary	Supplementary
		Estimand	Estimand
Handling rules	1-4	Treatment	Treatment
for ICEs		policy	policy
	5	Treatment	Treatment
		policy	policy
	6-7	Hypothetical	Treatment
			policy
	8-9	Hypothetical	Hypothetical

Table 6.3:1Handling rules for Intercurrent events

From the table above we see that that primary estimand estimates the treatment effect when changes to background CNS active medication, pharmacological SSRI therapies and non-pharmacological therapies (ICEs 1-5) are part of the treatment effect, but changes to randomized treatment (ICEs 6-9) are not considered to be part of the treatment effect of interest. ICEs are therefore handled by a hybrid estimand that combines the treatment policy and hypothetical approaches, where ICEs 1-5 are handled using the treatment policy approach, thus measurements taken after the occurrences of these ICEs are included in the primary analysis.

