However, ICEs 6-9 are handled using the hypothetical approach, where measurements after their occurrences are therefore censored in the primary analysis. Therefore, this analysis (ICEs 6-9) will include all data collected while on treatment which is defined as the time from the date of the first dose of trial medication until the date of the last dose of trial medication plus 7 days. Any data collected after a patient discontinues trial drug, regardless of reason, will be censored and will not be included in the primary analysis.

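### SAP Table 6.7:1 ends the Visit 10 window at last dose + 7 days, so it gives no Visit 10 slot to the off-treatment Week 8 values that its own eEOT note and the supplementary estimand call for

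*SAP*

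**What the plan says.** SAP 6.7, Table 6.7:1, gives Visits 2 to 9 windows in fixed study days. Visit 10/EOT has planned day "57 for completed subjects" and runs from Day 53 to "treatment stop date (stopdt) + 7 days". For patients who stop treatment early but keep providing efficacy data, the eEOT row says "those data points will be mapped to the later Visits as per the above Visit window", with an example in which a Day 46 CAPS-5 goes to Visit 8. The End of Trial row takes "stopdt + 8 days] to [stopdt + 30 days". Where a window holds several efficacy values, the analysis uses "the first one in the corresponding time window".

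The 7-day limit appears in two other places. The footnote to SAP Table 6.1:2 sets the residual effect period for efficacy ("and 7 days after last dose for efficacy"). SAP 6.3 defines on-treatment data for the primary analysis as running "until the date of the last dose of trial medication plus 7 days".

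SAP Table 6.3:1 "lists the handling of the ICEs for the primary estimand and supplementary estimand". ICEs 6-7 (withdrawal for drug-related adverse events, or for lack of efficacy or worsening) are hypothetical in the primary estimand and treatment policy in the supplementary one. ICEs 8-9 are hypothetical in both. Protocol 6.2.2 treats the Week 8 assessment of a discontinuer who stays in the study as that patient's Visit 10, and Protocol 3.3.4.1 asks discontinuers to attend it.

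**The concern.** The Visit 10 row uses an on-treatment limit as the edge of a visit window. These are separate things. The window says which visit a value belongs to; the limit says whether a given estimand uses the value. Visit 10 is the only later treatment-period visit whose window depends on the stop date, and it is the visit of the primary endpoint. The eEOT note therefore works for Visits 3 to 9 and fails at Week 8.

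What is at stake is the supplementary estimand for CAPS-5. Treatment policy for ICEs 6-7 is informative at Week 8 only if values taken after withdrawal enter at Week 8. The protocol collects them, but the mapping table gives them no Visit 10 slot. The same row governs PCL-5, although Protocol 7.2.4 analyses PCL-5 under the primary strategy. The visible SAP states no ICE strategy for the responder endpoints, so their need for such values is open.

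**Working it through.** Write *s* for the study day of the last dose and *d* for the day of the assessment.

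**Inputs**
- Visit 10 window: 53 ≤ d ≤ s + 7. End of Trial window: s + 8 ≤ d ≤ s + 30. Visit 6: Days 27-33. Visit 8: Days 41-47 (SAP Table 6.7:1).
- Scheduled Visit 10: Days 57 to 59 (protocol flow charts). eEOT: within 7 days of the last dose (Protocol 3.3.4.1).
- Primary inclusion limit: d ≤ s + 7 (SAP 6.3).
- Visits in the CAPS-5 model: 2, 6 and 10, with unstructured covariance (SAP 7.4.1).

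**1. The SAP's own example.** Day 31 lies in 27-33 (Visit 6) and Day 46 in 41-47 (Visit 8), so the example reproduces. An eEOT on Day 31 implies s = 24 to 31, hence s + 7 = 31 to 38. Day 46 is therefore off treatment. It also lies in the End of Trial window at both extremes (Days 32-54 for s = 24, Days 39-61 for s = 31). The SAP still assigns it to Visit 8. The intent is thus mapping by study day, with the nominal visit ahead of End of Trial. Yet this same patient's Visit 10 window would close on Day 31 to 38, before it opens on Day 53.

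**2. The Visit 10 row in general**
- Day 57 maps to Visit 10 if 57 ≤ s + 7, that is s ≥ 50.
- Day 59 maps if 59 ≤ s + 7, that is s ≥ 52.
- The window is empty if s + 7 < 53, that is s ≤ 45.
- An unmapped Day 57 value meets the End of Trial window if s + 8 ≤ 57 ≤ s + 30, that is s = 27 to 49. For s ≤ 26 it meets no window.

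**3. Overlap with the primary.** Every value that maps to Visit 10 satisfies d ≤ s + 7, which is also the primary's inclusion limit. So no Week 8 value can be kept by the supplementary analysis and censored in the primary.

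**4. What can still differ.** The Visit 6 window is fixed. A Day 29 value is off treatment if 29 > s + 7, that is s ≤ 21. After ICEs 6-7 such a value is censored in the primary and kept in the supplementary analysis. If the supplementary analysis uses the same model, the Week 4 value influences the Week 8 estimate through the covariance.

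**5. Checks on the fix**
- Upper bound: the primary now uses Days 53 to s + 7. With bound U it would use Days 53 to min(U, s + 7). For U = 65 the two agree whenever s ≤ 58. Day 58 is the latest scheduled last dose (EOT on Day 59, last dose the day before). U = 63 would lose Day 64 for s = 57 and Days 64-65 for s = 58. U = 59 would lose Days 60-63 for s = 56.
- Selection: the eEOT falls between s and s + 7. For s = 46 to 49 it can fall on Day 53 up to Day 53, 54, 55 and 56 respectively. The first-observation rule would then take it ahead of a Day 57 value.
- Order of steps: take an ICE 8 patient with last dose on Day 48, eEOT on Day 54 and Visit 10 on Day 57. The limit is Day 55, so Day 54 is usable and Day 57 is censored. Flagging before selecting keeps Day 54. Preferring the scheduled value for every discontinuer would lose it.

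**The case against.** The strongest reply is that the intent is already clear. The planned-day cell names completers, discontinuers have their own row, and the Day 46 example shows both study-day mapping and precedence over End of Trial. CAPS-5 and PCL-5 are not scheduled at follow-up (Flow Chart 2), so End of Trial is not a natural home for a Week 8 value. On this reading the table is incomplete, not contradictory. Most of this stands: it shows what the SAP meant and makes the correction small. It does not supply the missing rule, because the example stops at Visit 8, whose window is fixed, and no other Week 8 window is stated.

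The second reply is that the supplementary analysis may be specified elsewhere. The public SAP goes from 7.4.1 to 7.5 and cites a Section 10.1 that is not shown. An overriding rule could be there. This stands as a condition on the consequence, though not on the conflict between the visible row and note.

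Third, one might say that scheduled visits simply keep their nominal label. The sentence on nominal visits names only repeated and unscheduled measurements, but the rule of one observation per window covers all efficacy measurements, and the eEOT note applies windows to data after discontinuation.

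A reader might also infer that the two estimand analyses would coincide, so that their agreement would mean nothing. The documents do not support that: off-treatment Week 4 values could still separate them.

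**Conclusion.** The Visit 10 row is wrong as written and does not carry out the SAP's own mapping intent. Severity is minor. The consequence is limited to the supplementary estimand, which would gain no off-treatment Week 8 values and so be a weaker robustness check than planned. This assumes that no text outside the public SAP overrides the table.

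Two stronger inferences are not supported. The primary estimand does not lose data, because it censors at the same limit. Nor can the stop-day results be read as a share of patients. Of last-dose Days 1 to 55, 49 leave a Day 57 value outside the window, but that counts calendar days with equal weight. The documents give no rate for ICEs 6-7, no distribution of stop dates and no Week 8 return rate. The 30% drop-out in Protocol 7.5 is not broken down in any of these ways. Neither the number of patients affected nor the shift in the estimate can be computed.

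**What to change.** 1. Define the Visit 10 window for CAPS-5 and PCL-5 as Day 53 to Day 65, whatever the stop date.
2. State that nominal visit windows take precedence over End of Trial for efficacy data, as the Day 46 example already implies.
3. Use last dose + 7 days only as an estimand-specific censoring flag, set before the observation is selected: after ICEs 6-9 in the primary, and after ICEs 8-9 in the supplementary analysis.
4. In the supplementary analysis only, and for ICE 6-7 discontinuers only, use the scheduled Week 8 value when both it and an eEOT value fall in the window. Keep the first-observation rule everywhere else.

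The cost is one table row, two sentences and one derivation flag. No new data are needed, since the protocol already asks discontinuers to attend Visit 10. The primary data stay the same for any last dose up to Day 58, provided that the primary also keeps its last dose + 7 days limit for completers, as the on-treatment definition in SAP 6.3 implies. The change should be made before any unblinded analysis, including the interim, which uses the same estimands (Protocol 7.2.8).
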